**10.12.7.2. Final Analyses**

Safety: Tables					
No.	Population	IDSL / Example Shell	Title	Programming Notes	Deliverable
Adverse Events (AEs)					
3.61.	Safety 1	AE1	Summary of All Adverse Events by System Organ Class and Preferred Term in Overall Study Period	ICH E3 Treatment Emergent Three treatment arms (240, 400 and 240 + 400U)	SAC
3.62.	Safety 1	AE1	Summary of All Adverse Events by System Organ Class and Preferred Term in Blind Phase	Blind Phase (until second dose) See the Section 10.4.2. Two treatment arm (240 and 400U)	SAC

CONFIDENTIAL

207660

Safety: Tables					
No.	Population	IDSL / Example Shell	Title	Programming Notes	Deliverable
3.63.	Safety 1	AE1	Summary of All Adverse Events within 84 days from the initial dose by System Organ Class and Preferred Term in Blind Phase	Blind Phase (within 84 days) See the Section 10.4.2 . Two treatment arm (240 and 400U)	SAC
3.64.	Safety 2	AE1	Summary of All Adverse Events by System Organ Class and Preferred Term in Open Label Phase (2nd Treatment)	Open Label Phase (2nd Treatment) See the Section 10.4.2 . Three treatment arms (240, 400 and 240 + 400U)	SAC
3.65.	Safety 3	AE1	Summary of All Adverse Events by System Organ Class and Preferred Term in Open Label Phase (3rd Treatment)	Open Label Phase (3rd Treatment) See the Section 10.4.2 . Three treatment arms (240, 400 and 240 + 400U)	SAC
3.66.	Safety 4	AE1	Summary of All Adverse Events by System Organ Class and Preferred Term in Open Label Phase (4th Treatment)	Open Label Phase (4th Treatment) See the Section 10.4.2 . Three treatment arms (240, 400 and 240 + 400U)	SAC
3.67.	Safety 1	AE5A	Summary of All Adverse Events by Maximum Intensity by System Organ Class and Preferred Term in Overall Study Period	ICH E3 Treatment Emergent Three treatment arms (240, 400 and 240 + 400U)	SAC
3.68.	Safety 1	AE5A	Summary of All Adverse Events by Maximum Intensity by System Organ Class and Preferred Term in Blind Phase	Blind Phase (until second dose) See the Section 10.4.2 . Two treatment arm (240 and 400U)	SAC
3.69.	Safety 1	AE5A	Summary of All Adverse Events within 84 days from the initial dose by Maximum Intensity by System Organ Class and Preferred Term in Blind Phase	Blind Phase (within 84 days) See the Section 10.4.2 . Two treatment arm (240 and 400U)	SAC

CONFIDENTIAL

207660

Safety: Tables					
No.	Population	IDSL / Example Shell	Title	Programming Notes	Deliverable
3.70.	Safety 2	AE5A	Summary of All Adverse Events by Maximum Intensity by System Organ Class and Preferred Term in Open Label Phase (2nd Treatment)	Open Label Phase (2nd Treatment) See the Section 10.4.2 . Three treatment arms (240, 400 and 240 + 400U)	SAC
3.71.	Safety 3	AE5A	Summary of All Adverse Events by Maximum Intensity by System Organ Class and Preferred Term in Open Label Phase (3rd Treatment)	Open Label Phase (3rd Treatment) See the Section 10.4.2 . Three treatment arms (240, 400 and 240 + 400U)	SAC
3.72.	Safety 4	AE5A	Summary of All Adverse Events by Maximum Intensity by System Organ Class and Preferred Term in Open Label Phase (4th Treatment)	Open Label Phase (4th Treatment) See the Section 10.4.2 . Three treatment arms (240, 400 and 240 + 400U)	SAC
3.73.	Safety 1	AE3	Summary of Common (>=3%) Adverse Events by Overall Frequency in Overall Study Period	ICH E3 Treatment Emergent Three treatment arms (240, 400 and 240 + 400U)	SAC
3.74.	Safety 1	AE3	Summary of Common (>=3%) Adverse Events by Overall Frequency in Blind Phase	Blind Phase (until second dose) See the Section 10.4.2 . Two treatment arm (240 and 400U)	SAC
3.75.	Safety 1	AE3	Summary of Common (>=3%) Adverse Events within 84 days from the initial dose by Overall Frequency in Blind Phase	Blind Phase (within 84 days) See the Section 10.4.2 . Two treatment arm (240 and 400U)	SAC

CONFIDENTIAL

207660

Safety: Tables					
No.	Population	IDSL / Example Shell	Title	Programming Notes	Deliverable
3.76.	Safety 2	AE3	Summary of Common ( $\geq 3\%$ ) Adverse Events by Overall Frequency in Open Label Phase (2nd Treatment)	Open Label Phase (2nd Treatment) See the Section 10.4.2 . Three treatment arms (240, 400 and 240 + 400U)	SAC
3.77.	Safety 3	AE3	Summary of Common ( $\geq 3\%$ ) Adverse Events by Overall Frequency in Open Label Phase (3rd Treatment)	Open Label Phase (3rd Treatment) See the Section 10.4.2 . Three treatment arms (240, 400 and 240 + 400U)	SAC
3.78.	Safety 4	AE3	Summary of Common ( $\geq 3\%$ ) Adverse Events by Overall Frequency in Open Label Phase (4th Treatment)	Open Label Phase (4th Treatment) See the Section 10.4.2 . Three treatment arms (240, 400 and 240 + 400U)	SAC
3.79.	Safety 1	AE1	Summary of All Drug-Related Adverse Events by System Organ Class and Preferred Term in Overall Study Period	ICH E3 Treatment Emergent Three treatment arms (240, 400 and 240 + 400U)	SAC
3.80.	Safety 1	AE1	Summary of All Drug-Related Adverse Events by System Organ Class and Preferred Term in Blind Phase	Blind Phase (until second dose) See the Section 10.4.2 . Two treatment arm (240 and 400U)	SAC
3.81.	Safety 1	AE1	Summary of All Drug-Related Adverse Events within 84 days from the initial dose by System Organ Class and Preferred Term in Blind Phase	Blind Phase (within 84 days) See the Section 10.4.2 . Two treatment arm (240 and 400U)	SAC

CONFIDENTIAL

207660

Safety: Tables					
No.	Population	IDSL / Example Shell	Title	Programming Notes	Deliverable
3.82.	Safety 2	AE1	Summary of All Drug-Related Adverse Events by System Organ Class and Preferred Term in Open Label Phase (2nd Treatment)	Open Label Phase (2nd Treatment) See the Section 10.4.2 . Three treatment arms (240, 400 and 240 + 400U)	SAC
3.83.	Safety 2	AE1	Summary of All Drug-Related Adverse Events by System Organ Class and Preferred Term in Open Label Phase (3rd Treatment)	Open Label Phase (3rd Treatment) See the Section 10.4.2 . Three treatment arms (240, 400 and 240 + 400U)	SAC
3.84.	Safety 2	AE1	Summary of All Drug-Related Adverse Events by System Organ Class and Preferred Term in Open Label Phase (4th Treatment)	Open Label Phase (4th Treatment) See the Section 10.4.2 . Three treatment arms (240, 400 and 240 + 400U)	SAC
3.85.	Safety 1	AE5A	Summary of All Drug-Related Adverse Events by System Organ Class and Preferred Term and Maximum Intensity in Overall Study Period	ICH E3 Treatment Emergent AE See the Section 10.4.2 Three treatment arms (240, 400 and 240 + 400U)	SAC
3.86.	Safety 1	AE5A	Summary of All Drug-Related Adverse Events by System Organ Class and Preferred Term and Maximum Intensity in Blind Phase	Blind Phase (until second dose) See the Section 10.4.2 . Two treatment arm (240 and 400U)	SAC
3.87.	Safety 1	AE5A	Summary of All Drug-Related Adverse Events within 84 days from the initial dose by System Organ Class and Preferred Term and Maximum Intensity in Blind Phase	Blind Phase (within 84 days) See the Section 10.4.2 . Two treatment arm (240 and 400U)	SAC

CONFIDENTIAL

207660

Safety: Tables					
No.	Population	IDSL / Example Shell	Title	Programming Notes	Deliverable
3.88.	Safety 2	AE5A	Summary of All Drug-Related Adverse Events by System Organ Class and Preferred Term and Maximum Intensity in Open Label Phase (2nd Treatment)	Open Label Phase (2nd Treatment) See the Section 10.4.2 . Three treatment arms (240, 400 and 240 + 400U)	SAC
3.89.	Safety 2	AE5A	Summary of All Drug-Related Adverse Events by System Organ Class and Preferred Term and Maximum Intensity in Open Label Phase (3rd Treatment)	Open Label Phase (3rd Treatment) See the Section 10.4.2 . Three treatment arms (240, 400 and 240 + 400U)	SAC
3.90.	Safety 2	AE5A	Summary of All Drug-Related Adverse Events by System Organ Class and Preferred Term and Maximum Intensity in Open Label Phase (4th Treatment)	Open Label Phase (4th Treatment) See the Section 10.4.2 Three treatment arms (240, 400 and 240 + 400U)	SAC
3.91.	Safety 1	AE3	Summary of Most Common Serious Drug Related Adverse Events by Overall Frequency in Overall Study Period	Three treatment arms (240, 400 and 240 + 400U)	SAC
3.92.	Safety 1	AE2	Summary of Most Common Non-Serious Drug Related Adverse Events by Overall Frequency in Overall Study Period	Three treatment arms (240, 400 and 240 + 400U)	SAC
3.93.	Safety 1	AE15	Summary of Common (>=5%) Non-serious Adverse Events by System Organ Class and Preferred Term (Number of Participant and Occurrences) in Overall Study Period	FDAAA, EudraCT Treatment Emergent AE See the Section 10.4.2 Three treatment arms (240, 400 and 240 + 400U)	SAC

CONFIDENTIAL

207660

Safety: Tables					
No.	Population	IDSL / Example Shell	Title	Programming Notes	Deliverable
Serious and Other Significant Adverse Events					
3.94.	Safety 1	SAFE_T1	Summary of Adverse Events of Special Interest in Overall Study Period	Treatment Emergent AE See the Section 10.4.2 Three treatment arms (240, 400 and 240 + 400U)	SAC
3.95.	Safety 1	SAFE_T1	Summary of Adverse Events of Special Interest in Blind Phase	Blind Phase (until second dose) See the Section 10.4.2 . Two treatment arm (240 and 400U)	SAC
3.96.	Safety 1	SAFE_T1	Summary of Adverse Events of Special Interest within 84 days from the initial dose in Blind Phase	Blind Phase (within 84 days) See the Section 10.4.2 . Two treatment arm (240 and 400U)	SAC
3.97.	Safety 2	SAFE_T1	Summary of Adverse Events of Special Interest in Open Label Phase (2nd Treatment)	Open Label Phase (2nd Treatment) See the Section 10.4.2 Three treatment arms (240, 400 and 240 + 400U)	SAC
3.98.	Safety 3	SAFE_T1	Summary of Adverse Events of Special Interest in Open Label Phase (3rd Treatment)	Open Label Phase (3rd Treatment) See the Section 10.4.2 Three treatment arms (240, 400 and 240 + 400U)	SAC
3.99.	Safety 4	SAFE_T1	Summary of Adverse Events of Special Interest in Open Label Phase (4th Treatment)	Open Label Phase (4th Treatment) See the Section 10.4.2 Three treatment arms (240, 400 and 240 + 400U)	SAC

CONFIDENTIAL

207660

Safety: Tables					
No.	Population	IDSL / Example Shell	Title	Programming Notes	Deliverable
3.100.	Safety 1	AE1	Summary of Non-Fatal Serious Adverse Events in Overall Study Period	Treatment Emergent AE See the Section 10.4.2 Three treatment arms (240, 400 and 240 + 400U)	SAC
3.101.	Safety 1	AE1	Summary of Non-Fatal Serious Adverse Events in Blind Phase	Blind Phase (until second dose) See the Section 10.4.2 . Two treatment arm (240 and 400U)	SAC
3.102.	Safety 1	AE1	Summary of Non-Fatal Serious Adverse Events within 84 days from the initial dose in Blind Phase	Blind Phase (within 84 days) See the Section 10.4.2 . Two treatment arm (240 and 400U)	SAC
3.103.	Safety 2	AE1	Summary of Non-Fatal Serious Adverse Events in Open Label Phase (2nd Treatment)	Open Label Phase (2nd Treatment) See the Section 10.4.2 Three treatment arms (240, 400 and 240 + 400U)	SAC
3.104.	Safety 3	AE1	Summary of Non-Fatal Serious Adverse Events in Open Label Phase (3rd Treatment)	Open Label Phase (3rd Treatment) See the Section 10.4.2 Three treatment arms (240, 400 and 240 + 400U)	SAC
3.105.	Safety 4	AE1	Summary of Non-Fatal Serious Adverse Events in Open Label Phase (4th Treatment)	Open Label Phase (4th Treatment) See the Section 10.4.2 Three treatment arms (240, 400 and 240 + 400U)	SAC

CONFIDENTIAL

207660

Safety: Tables					
No.	Population	IDSL / Example Shell	Title	Programming Notes	Deliverable
3.106.	Safety 1	AE1	Summary of Drug-Related Non-Fatal Serious Adverse Events in Overall Study Period	Treatment Emergent AE See the Section 10.4.2 Three treatment arms (240, 400 and 240 + 400U)	SAC
3.107.	Safety 1	AE1	Summary of Drug-Related Non-Fatal Serious Adverse Events in Blind Phase	Blind Phase (until second dose) See the Section 10.4.2 . Two treatment arm (240 and 400U)	SAC
3.108.	Safety 1	AE1	Summary of Drug-Related Non-Fatal Serious Adverse Events within 84 days from the initial dose in Blind Phase	Blind Phase (within 84 days) See the Section 10.4.2 . Two treatment arm (240 and 400U)	SAC
3.109.	Safety 2	AE1	Summary of Drug-Related Non-Fatal Serious Adverse Events in Open Label Phase (2nd Treatment)	Open Label Phase (2nd Treatment) See the Section 10.4.2 Three treatment arms (240, 400 and 240 + 400U)	SAC
3.110.	Safety 3	AE1	Summary of Drug-Related Non-Fatal Serious Adverse Events in Open Label Phase (3rd Treatment)	Open Label Phase (3rd Treatment) See the Section 10.4.2 Three treatment arms (240, 400 and 240 + 400U)	SAC
3.111.	Safety 4	AE1	Summary of Drug-Related Non-Fatal Serious Adverse Events in Open Label Phase (4th Treatment)	Open Label Phase (4th Treatment) See the Section 10.4.2 Three treatment arms (240, 400 and 240 + 400U)	SAC

CONFIDENTIAL

207660

Safety: Tables					
No.	Population	IDSL / Example Shell	Title	Programming Notes	Deliverable
3.112.	Safety 1	AE16	Summary of Serious Adverse Events by System Organ Class and Preferred Term (Number of Participants and Occurrences) in Overall Study Period	FDAAA, EudraCT Treatment Emergent AE See the Section 10.4.2 Three treatment arms (240, 400 and 240 + 400U)	SAC
3.113.	Safety 1	AE1	Summary of Adverse Events Leading to Withdrawal from Study by System Organ Class and Preferred Term in Overall Study Period	IDSL Treatment Emergent AE See the Section 10.4.2 Three treatment arms (240, 400 and 240 + 400U)	SAC
3.114.	Safety 1	AE1	Summary of Adverse Events Leading to Withdrawal from Study by System Organ Class and Preferred Term in Blind Phase	Blind Phase (until second dose) See the Section 10.4.2 . Two treatment arm (240 and 400U)	SAC
3.115.	Safety 1	AE1	Summary of Adverse Events Leading to Withdrawal from Study within 84 days from the initial dose by System Organ Class and Preferred Term in Blind Phase	Blind Phase (within 84 days) See the Section 10.4.2 . Two treatment arm (240 and 400U)	SAC
3.116.	Safety 2	AE1	Summary of Adverse Events Leading to Withdrawal from Study by System Organ Class and Preferred Term in Open Label Phase (2nd Treatment)	Open Label Phase (2nd Treatment) See the Section 10.4.2 . Three treatment arms (240, 400 and 240 + 400U)	SAC
3.117.	Safety 3	AE1	Summary of Adverse Events Leading to Withdrawal from Study by System Organ Class and Preferred Term in Open Label Phase (3rd Treatment)	Open Label Phase (3rd Treatment) See the Section 10.4.2 . Three treatment arms (240, 400 and 240 + 400U)	SAC

CONFIDENTIAL

207660

Safety: Tables					
No.	Population	IDSL / Example Shell	Title	Programming Notes	Deliverable
3.118.	Safety 4	AE1	Summary of Adverse Events Leading to Withdrawal from Study by System Organ Class and Preferred Term in Open Label Phase (4th Treatment)	Open Label Phase (4th Treatment) See the Section 10.4.2. Three treatment arms (240, 400 and 240 + 400U)	SAC
Laboratory: Chemistry					
3.119.	Safety 1	LB1	Summary of Chemistry by Visit	Summarize data at Screening Visit, in Blind Phase and at Final Visit.	SAC
3.120.	Safety 1	LB1	Summary of Chemistry Changes from Baseline by Visit	Summarize data in Blind Phase and at Final Visit. ICH E3	SAC
3.121.	Safety 1	LB3	Summary of Chemistry Shifts from Baseline Relative to Normal Range		SAC
3.122.	Safety 1	LB15	Summary of Worst Case Chemistry Results Relative to Normal Range Post-Baseline Relative to Baseline	ICH E3	SAC
Laboratory: Hematology					
3.123.	Safety 1	LB1	Summary of Hematology by Visit	Summarize data at Screening Visit, in Blind Phase and at Final Visit.	SAC
3.124.	Safety 1	LB1	Summary of Hematology Changes from Baseline	Summarize data in Blind Phase and at Final Visit. ICH E3	SAC
3.125.	Safety 1	LB3	Summary of Hematology Shifts from Baseline Relative to Normal Range		SAC
3.126.	Safety 1	LB15	Summary of Worst Case Hematology Results Relative to Normal Range Post-Baseline Relative to Baseline	ICH E3	SAC

CONFIDENTIAL

207660

Safety: Tables					
No.	Population	IDSL / Example Shell	Title	Programming Notes	Deliverable
Laboratory: Urinalysis					
3.127.	Safety 1	UR1	Summary of Worst Case Urinalysis Results (Discrete or Character Values) Post-Baseline Relative to Baseline	ICH E3	SAC
Laboratory: Hepatobiliary (Liver)					
3.128.	Safety 1	LIVER1	Summary of Liver Monitoring/Stopping Event Reporting	This display will be presented if liver events occur.	SAC
3.129.	Safety 1	LIVER10	Summary of Hepatobiliary Laboratory Abnormalities	IDSL	SAC
ECG					
3.130.	Safety 1	EG1	Summary of ECG Findings	Summarize data at Screening Visit, in Blind Phase and at Final Visit. IDSL	SAC
3.131.	Safety 1	EG2	Summary of ECG Values	Summarize data at Screening Visit, in Blind Phase and at Final Visit.	SAC
3.132.	Safety 1	EG2	Summary of Change from Baseline in ECG Values by Visit	Summarize data in Blind Phase and at Final Visit. IDSL	SAC
Vital Signs					
3.133.	Safety 1	VS1	Summary of Vital Signs	Summarize data at Screening Visit, in Blind Phase and at Final Visit.	SAC
3.134.	Safety 1	VS1	Summary of Change from Baseline in Vital Signs	Summarize data in Blind Phase and at Final Visit. ICH E3	SAC

CONFIDENTIAL

207660

Safety: Tables					
No.	Population	IDSL / Example Shell	Title	Programming Notes	Deliverable
SpO2					
3.135.	Safety 1	SAFE_T1	Summary of Value and Change from Baseline in SpO2		SAC
Exposure and Treatment Compliance					
3.136.	Safety 1	SAFE_T3	Summary of Exposure to Study Treatment	ICH E3	SAC
3.137.	Safety 1	SAFE_T4	Summary of Extent of Exposure to Study Treatment by Treatment Cycle and Muscle Region	Include total arm in Open label phase only	SAC
3.138.	Safety 1	SAFE_T4	Summary of Extent of Exposure to Study Treatment by Treatment Cycle and Joint	Include total arm in Open label phase only	SAC

CONFIDENTIAL

207660

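### Four final-analysis tables of drug-related AEs in the 3rd and 4th treatment cycles use Safety 2, so their percentages include participants who never received that treatment

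*SAP*

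**What the plan says.** Section 4 of the amended SAP defines nested safety populations. Safety 2 is treated at least twice, Safety 3 at least three times, and Safety 4 four times. The note under that section refers to Appendix 12 for the population of each display.

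In Appendix 12 (Section 10.12.7.2) the four drug-related AE tables for the later cycles read:

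- "3.83. Safety 2 AE1 Summary of All Drug-Related Adverse Events by System Organ Class and Preferred Term in Open Label Phase (3rd Treatment"
- "3.84. Safety 2 AE1 Summary of All Drug-Related Adverse Events by System Organ Class and Preferred Term in Open Label Phase (4th Treatment"
- "3.89. Safety 2 AE5A Summary of All Drug-Related Adverse Events by System Organ Class and Preferred Term and Maximum Intensity in Open Label Phase (3rd"
- "3.90. Safety 2 AE5A Summary of All Drug-Related Adverse Events by System Organ Class and Preferred Term and Maximum Intensity in Open Label Phase (4th"

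The matching all-AE tables for the same cycles read "3.65. Safety 3 AE1 Summary of All Adverse Events by System Organ Class and Preferred Term in Open Label Phase (3rd Treatment" and "3.66. Safety 4 AE1 Summary of All Adverse Events by System Organ Class and Preferred Term in Open Label Phase (4th Treatment". The drug-related serious AE table for the 3rd treatment reads "3.110. Safety 3 AE1 Summary of Drug-Related Non-Fatal Serious Adverse Events in Open Label Phase (3rd Treatment", and its 4th-treatment partner, Table 3.111, uses Safety 4.

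Section 8.1 says that these displays give numbers and percentages of participants with at least one event, by treatment group. Section 10.4.2 starts the 3rd- and 4th-treatment AE windows at the date of the 3rd and 4th injection. Section 2.3 makes each further injection conditional on the investigator confirming eligibility.

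**The concern.** A percentage of participants with an event in a cycle should be taken over those exposed in that cycle. Safety 2 also includes participants who stopped after two treatments and, for the 4th-cycle tables, those who stopped after three. By the SAP's own windows they cannot have an event in the cycle being tabulated. They can only lower the percentage.

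Three things are at stake, all in the description of repeated 400-unit exposure, which falls under a stated secondary objective (Section 2.2):

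- The drug-related percentage in these four tables is too low.
- It has a different denominator from the all-AE percentage in the same cycle, so the proportion of AEs judged drug-related cannot be read across the tables.
- Within the drug-related series, cycle 2 has the right denominator and cycles 3 and 4 do not. An apparent fall across cycles could arise from the denominators alone.

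**Working it through.** The SAP states no figure to reproduce. The check is a comparison of entries, followed by denominator arithmetic.

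**1. Population column, final analyses, 3rd / 4th treatment**

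| Content | Tables | Populations |
|---|---|---|
| All AEs | 3.65 / 3.66 | Safety 3 / Safety 4 |
| All AEs by maximum intensity | 3.71 / 3.72 | Safety 3 / Safety 4 |
| Common AEs | 3.77 / 3.78 | Safety 3 / Safety 4 |
| **Drug-related AEs** | **3.83 / 3.84** | **Safety 2 / Safety 2** |
| **Drug-related AEs by maximum intensity** | **3.89 / 3.90** | **Safety 2 / Safety 2** |
| AEs of special interest | 3.98 / 3.99 | Safety 3 / Safety 4 |
| Non-fatal SAEs | 3.104 / 3.105 | Safety 3 / Safety 4 |
| Drug-related non-fatal SAEs | 3.110 / 3.111 | Safety 3 / Safety 4 |
| AEs leading to withdrawal | 3.117 / 3.118 | Safety 3 / Safety 4 |

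The first RAP version had the same four entries (its Tables 3.79, 3.80, 3.85 and 3.86). The amendment log in Section 1.1 gives no reason for them, although it does correct another table's population (race, from Enrolled to ITT1).

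**2. Effect on a percentage.** With x participants having an event in cycle k:

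- reported % = 100·x / N(Safety 2)
- correct % = 100·x / N(Safety k)
- reported / correct = N(Safety k) / N(Safety 2) ≤ 1

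Equality holds only if everyone treated twice also receives treatment k. The ratio applies separately to each displayed column (240, 400 and combined).

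**3. Range without a model for retreatment.** Take both arms combined, Safety 2 = 120 (the maximum, all randomized) and x = 3. The reported value is 3/120 = 2.5%. If 90%, 70%, 50%, 30% or 10% of Safety 2 received the treatment in question, the correct value is 3/108 = 2.8%, 3/84 = 3.6%, 3/60 = 5.0%, 3/36 = 8.3% or 3/12 = 25.0%.

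**4. Illustration tied to the schedule.** Eligibility is evaluated at Week 12 after each injection and every 4 weeks after that, and not after Week 36 from the first injection (Section 10.2.1). Assume the same independent probability q of qualifying at each evaluation, q = 0.5 to 0.7, and no withdrawals.

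- Safety 2: at least one success in seven evaluations (Weeks 12, 16, 20, 24, 28, 32, 36). Share = 1 − (1−q)^7 = 0.992 for q = 0.5 and 0.9998 for q = 0.7.
- Safety 3: two cycles must fit into 36 weeks. Since 12 + 12 = 24, at most three failed evaluations are allowed. Share = q²·[1 + 2(1−q) + 3(1−q)² + 4(1−q)³]. For q = 0.5 this is 0.25 × 3.25 = 0.8125. For q = 0.7 it is 0.49 × 1.978 = 0.969.
- Safety 4: 12 + 12 + 12 = 36, so no failed evaluation is allowed. Share = q³ = 0.125 or 0.343, which is 15 or 41 of 120.

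Reported / correct:

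- 3rd cycle: 0.8125/0.992 = 0.82 and 0.969/0.9998 = 0.97, so about 18% to 3% too low.
- 4th cycle: 0.125/0.992 = 0.126 and 0.343/0.9998 = 0.343, so understated 7.9-fold to 2.9-fold. Three affected participants would show as about 2.5% instead of 3/15 = 20% or 3/41 = 7.3%.

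**5. Coherence between tables.** Drug-related SAEs are a subset of drug-related AEs. With Safety 4 = 41 and Safety 2 = 120 (the q = 0.7 case), one participant whose only 4th-cycle drug-related AE is a non-fatal SAE appears as 1/41 = 2.4% in Table 3.111 and 1/120 = 0.8% in Table 3.84. The subset would show a higher percentage than the set containing it.

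**The case against.** The case for leaving this alone, or giving it little weight, is that these are four descriptive tables in a study that tests no hypothesis (Sections 2.4 and 5.5). The numerators are right. Table 1.17 summarises the populations and Tables 3.65 and 3.66 use the right denominators, so a reader can recompute the percentages. The displays that matter most for safety (special interest, serious, drug-related serious, withdrawals) already use Safety 3 and Safety 4. The overall drug-related Table 3.79 is on Safety 1, and Listing 53 gives every AE with its study phase. All of this stands, and it limits the weight of the point. It does not justify the entries: nothing in the SAP corrects or explains them, and the general reference in Section 8 to Safety 1, 2, 3 and 4 does not override a table-level assignment.

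The size is also open to challenge, and rightly. The independence model uses one q for everyone. If some participants habitually requalify at Week 12, the average of q³ exceeds the cube of the average q, so Safety 4 is larger and the 4th-cycle dilution smaller. Withdrawals are ignored. The SAP gives no counts for Safety 2, 3 or 4.

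Two stronger readings are tempting. A reader might infer that drug-related risk under repeated 400-unit dosing is understated throughout the report. The documents support that only for the percentages in these four tables. A reader might also take the several-fold 4th-cycle figure as established, or extend it to the 3rd cycle. It is an assumption-based illustration, and under the same assumption the 3rd-cycle effect is modest.

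**Conclusion.** The four entries are wrong as written: an internal inconsistency that looks like a copy-forward slip, not an analysis choice. The direction follows from the SAP's own definitions. The percentages can only be too low, by the factor N(Safety k)/N(Safety 2), unless everyone treated twice also receives the later treatment. They are also not comparable with the all-AE and drug-related SAE percentages for the same cycle.

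The size cannot be derived from the SAP. With a 50-70% independent chance of qualifying at each evaluation visit and no withdrawals, it is about 3-18% for the 3rd cycle and about 3- to 8-fold for the 4th. The 4th-cycle effect is the larger because the schedule admits only those who qualify at Week 12 in all three earlier cycles. This should be fixed, but it does not threaten the trial's conclusions: counts, interim tables and the primary efficacy analysis are untouched.

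**What to change.** In Section 10.12.7.2, change the population of Tables 3.83 and 3.89 to Safety 3, and of Tables 3.84 and 3.90 to Safety 4. Record the correction in the amendment log, as was done for the race table.

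The cost is four cells in the list of displays and the matching population setting in four programs. No data collection, method or timeline changes.
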